10.3 Therapy After Protocol Treatment is Stopped

At the discretion of the investigator.

11.0 CENTRAL REVIEW PROCEDURES

11.1 Central Radiology Review

There will be no central radiology review for this study.

11.2 Central Pathology Review

There will be no central pathology review for this study.

12.0 CORRELATIVE STUDIES

Tissue samples collected on this trial may be used by researchers now or in the future to better understand the nature of colorectal cancer and how patients respond to treatment. Samples will be used for research purposes only and will not be sold. A scientific review process of any proposals to use the tissue will take place and any proposals approved will have undergone ethics approval. Patients will not be identified by name. The only identification of tissue will be by a tumour banking code assigned at the time of sample receipt. Material issued to researchers will be anonymized and only identified by tumour banking coded number.

Specific samples to be collected and priority assays are as follows:

12.1 Protocol-Mandated Correlative Studies

Archival FFPE Tumour Tissue Submission (Mandatory)

Archival Tumour Block/Slides:

The submission of a representative block of the diagnostic tumour tissue (from primary or metastatic tumour) and the adjacent normal tissue (part of the standard resection) is mandatory for participation on this trial. Blocks will be carefully stored as part of the CCTG Tumour Tissue Data Repository at Queen's University in Kingston, Ontario, but the only assays done will be as part of this study. All patients on whom a diagnostic tumour block is collected will be aware of this retrieval and will have given their consent.

Blocks are the preferred material to collect, as it is well known that tissue materials (including protein and nucleic acid integrity) on unstained sections deteriorate rapidly within 3-6 months after preparation. One of the objectives will be to create tissue micro arrays. These will optimize the amount of tissue available to investigators and permit the preservation of the tumour block submitted.

If, at any time, the submitting hospital requires the block to be returned for medical or legal concerns, it will be returned by courier on request.

Samples will be used for research purposes only and will not be sold. Patients will not be identified by name. The only identification of tissue will be by a patient study number assigned at the time of registration to the trial, the surgical/ histology number and/or patient initials. Material issued to researchers will be anonymized and only identified by a coded number.

Testing specifically for hereditary genetic defects predisposing to malignant disease will not be carried out without the expressed consent of the patient.

Where no previously resected or biopsied tumour tissue exists, additional biopsy of the primary or metastatic tumour will be required.

Directions:

At the same time that the baseline form is submitted, original tumour block should be sent to the CCTG Pathology Coordinator. Centres should contact CCTG if they are unable to submit a tumour block, as sufficient tissue is required for the assays described above.

Within 4 weeks of randomization (note: a request letter will not be sent), complete the EDC Archival Tumour Tissue Submission Form. Print a copy of the completed form and ship tumour blocks/slides along with a Request for Payment form to:

[name]
Pathology Coordinator, Canadian Cancer Trials Group
[name]
[name]
Queen's University
[name]
[contact]
[contact]
Email: [contact]

Detailed instructions for FFPE sample acquisition, preparation, and shipping are found in the CO.26 Lab Manual.

Planned priority assays on archival tumour tissue include:

- Immunohistochemistry for PD-L1 and CTLA-4 expression;
- Immunohistochemistry for tumour infiltrating lymphocytes (CD8+ T cells);
- Other exploratory analysis by IHC and/or flow cytometry for more detailed characterization of immune cell population / additional immune markers (IDO, CD4, CD3, FOXP3);
- Immunohistochemistry for mismatch repair (MMR) proteins;
- Genomic instability measured by MSI assays or using SNP arrays;
- Mutational load measured using targeted next generation sequencing;
- Expression profiling to identify microsatellite instability immune, canonical, metabolic and mesenchymal subtypes of tumour.

Blood, Serum and Plasma Collection:

The CCTG is interested in exploring the use of surrogate tissues such as serum and plasma in evaluating potential prognostic or predictive biomarkers, or as evidence of pharmacodynamic effects. Blood, serum and plasma samples will be collected and banked for planned studies from all patients.

Planned priority assays on blood, serum and plasma include:

- Circulating tumour DNA

Detailed instructions for blood, serum and plasma sample acquisition, preparation, and shipping are found in the CO.26 Lab Manual.

12.2 Optional Banking of Samples

Banking of Tumour Tissue:

Mandatory submission of tumour tissue has been described above. The subsequent banking of collected diagnostic tissue is not mandatory for participation in the study, but the participation of all centres is strongly encouraged. Blocks and blood will be carefully banked as part of the CCTG tissue/tumour bank at Queen's University in Kingston, Ontario.

After patient consent, collection of paraffin tumour blocks will be preferred, as one of the objectives will be to create tissue micro arrays. These will optimize the amount of tissue available to investigators and permit the preservation of the tumour block submitted. If tumour blocks are unavailable, then two x 2 mm cores of tumour from the block and 30 specimen slides are preferred. If, at any time, the submitting hospital requires the block to be returned for medical or legal concerns, it will be returned by courier on request.

Proposals to use the banked specimens for the purposes of assessing markers involved in predicting treatment response and outcomes may be submitted to the bank. A scientific review process of any proposals to use the tissue will take place and any proposals approved will have undergone ethics approval.

Banking of Blood, Serum, and Plasma:

Mandatory submission of whole blood, serum, and plasma has been described above. The subsequent banking of collected samples is not mandatory for participation in the study, but the participation of all centres is strongly encouraged. Samples will be carefully banked as part of the CCTG tissue/tumour bank at Queen's University in Kingston, Ontario.

Proposals to use the banked specimens for the purposes of assessing markers involved in predicting treatment response and outcomes may be submitted to the bank. A scientific review process of any proposals to use the tissue will take place and any proposals approved will have undergone ethics approval.

13.0 STATISTICAL CONSIDERATIONS

13.1 Objectives and Design

The primary objective of this phase II randomized study is to assess the effect of the combination of durvalumab and tremelimumab and best supportive care (BSC) on the Overall Survival of patients with refractory, advanced colorectal cancer. Patients will be randomized to receive either combination of durvalumab and tremelimumab plus best supportive care, or best supportive care only in a 2:1 ratio after stratification by ECOG performance status (0 versus 1). Secondary objectives include comparisons of Progression Free Survival, Objective Response Rate, and Adverse Events between the two treatment arms.

13.2 Study Endpoints and Analysis

Overall Survival:

Overall Survival, the primary endpoint of this study, is defined as the time from randomization to death from any cause. Patients who are alive at the time of the final analysis or who have become lost to follow-up will be censored at their last date known to be alive. Patients will be analyzed in the arm to which they are randomized regardless of the treatment they received (intent-to-treat analysis). The survival experience of patients in both treatment groups will be summarized by the Kaplan-Meier method and compared primarily by a stratified log-rank test adjusting for the stratification variable (ECOG performance status and site of tumour) at randomization. Secondary analyses based on stratified Cox proportional hazards model will also be performed. ECOG performance status (0 versus 1) and site of tumour (right colon, transverse colon, left colon, rectum, unknown) will be the stratification factors to define the stratified Cox proportional hazards model. Besides the treatment factor (combination of durvalumab and tremelimumab + BSC versus BSC alone), the following factors at patient entry will be included in the stratified Cox proportional hazards model:

- Age (< 65 versus \geq 65)
- Sex (male versus female)
- Number of organ sites involved at baseline (\leq 2 versus $>$ 2)
- Presence of liver metastases (yes versus no)

A formal pre-planned subset analysis for the primary endpoint (OS) will be conducted to address the benefit of combination of durvalumab and tremelimumab between the groups defined by the above factors and the following:

- ECOG Performance Status (0 versus 1)
- Race (white, black, Asian, other)
- Site of tumour: (right colon, transverse colon, left colon, rectum)

Progression-Free Survival:

Progression-Free Survival (PFS) is defined as the time from randomization to the first objective documentation of disease progression or death due to any cause. If a patient has not progressed or died at the time of final analysis, PFS will be censored on the date of the last tumour assessment. This includes patients who are lost to follow-up or have withdrawn consent. All analyses for OS will also be performed for PFS, using similar methodology. A sensitivity analysis of PFS will also be performed where PFS is defined as the time from randomization to the second documentation of unequivocal disease progression in those patients who continued study therapy beyond the first objective documentation of disease progression and with interim CR, PR or SD documented.

Objective Response Rate:

Objective Response Rate (ORR) is defined as the proportion of patients with a documented complete response and partial response based on RECIST 1.1. The primary estimate of ORR will be based on all patients randomized. A Cochran-Mantel-Haenszel test adjusting for the stratification factors (ECOG performance status, site of tumour) at the time of randomization will be used to compare the objective response rates between two arms. A sensitivity analysis of ORR will also be performed where response is defined as the proportion of patients with a documented complete response and partial response based on RECIST 1.1 and/or Immune-Related Response Criteria (irRC) [Wolchok 2009].

Safety Analysis:

All patients who have received at least one dose of protocol treatment will be included in the safety analysis. The incidence of adverse events will be summarized by type of adverse event and severity using the NCI Common Terminology Criteria for Adverse Events. A Fisher's exact test will be used to compare adverse events between the two arms if required.

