5.1 Patient Evaluation Flowsheet: Pre-study (Baseline) and Post-randomization Follow-up
For Patients Randomized to Best Supportive Care (Arm 1)

| Required Investigations | PRE-STUDY (≤ 14 days prior to randomization, unless otherwise indicated) | PRIOR to objective disease progression (timing from randomization) | | AFTER objective disease progression (timing from randomization) |
|---|---|---|--|--|
| | | Every 4 weeks until objective disease progression | Every 8 weeks until objective disease progression (maintain schedule even if clinic visits are delayed) ³ | Every 12 weeks |
| History and Physical Exam | | | | |
| Including: height (baseline only), weight, ECOG performance status, clinical tumour measurements (if applicable) | X | X | | |
| Vital Signs (blood pressure, heart rate, temperature) | X | X | | |
| Concomitant Medications | X | X | | |
| Overall Survival | | | | |
| Survival Status Assessment | | X | X | X ¹ |
| Hematology | | | | |
| CBC, differential (including lymphocytes), platelets | X | X | | |
| Coagulation | | | | |
| PTT, PT/INR | X | X | | |
| Biochemistry | | | | |
| Serum Creatinine, Chloride, Sodium, Potassium, Calcium, Magnesium, Bilirubin, ALP, AST and ALT, LDH, Albumin, TSH ² , Amylase, Lipase, Serum CEA | X | X | | |
| Creatinine Clearance (calculated) | X | as clinically indicated | | |
| Glucose | X | as clinically indicated | | |
| Radiology³ | | | | |
| Chest/abdomen/pelvis CT or MRI scan ³ | X ≤ 28 days | | X ³ | |
| Other scans as necessary to document all measurable and non-measurable disease ³ | X ≤ 28 days | | | |
| Other Investigations | | | | |
| Pregnancy Test ⁴ | X | | | |
| ECG | X | as clinically indicated | | |
| Dipstick Urinalysis (including protein, specific gravity, glucose and blood) | X | | | |

table continued on next page ...

| Correlative Studies | | | |
|--|--|---|--|
| Archival Tissue Sample ⁵ (mandatory) | Availability of sufficient tissue must be confirmed prior to randomization | Submit tissue within 4 weeks of randomization | |
| Whole blood, plasma and serum ^{5,6} (mandatory) | X | To be done at 8 weeks, and at the time of objective disease progression ⁷ , if not already done | |
| Adverse Events | | | |
| Adverse Event Assessment ⁸ | X (To document residual adverse events from previous therapy and baseline symptoms) | X To be evaluated continuously for adverse events (until objective disease progression) | |
| Quality of Life | | | |

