7.1 Protocol Treatment Plan

7.1.1 Drug Administration

Patients will be randomized at a 2:1 ratio to receive durvalumab plus tremelimumab plus best supportive care or best supportive care only to a planned sample size of 180.

Best supportive care is defined as those measures designed to provide palliation of symptoms and improve quality of life as much as possible.

When durvalumab is given with tremelimumab, tremelimumab will be administered first. Durvalumab will start immediately after the tremelimumab infusion (during the post-tremelimumab observation period).

One cycle will be defined as 28 days (4 weeks). Study drugs will be started on cycle 1. Tremelimumab will only be given for the first 4 cycles.

| Arm | Agent(s) | Dose | Route | Duration* (infusion) | Schedule |
|-----|----------------------|---------|-------|----------------------|---------------------|
| 1 | Best Supportive Care | NA | NA | NA | NA |
| 2 | Tremelimumab | 75 mg | IV | 60 minutes | Day 1, cycles 1-4 |
| | Durvalumab | 1500 mg | IV | 60 minutes | Day 1 every 28 days |
| | Best Supportive Care | NA | NA | NA | NA |

* Duration (overall) of durvalumab and tremelimumab is until unequivocal progression or unacceptable toxicity.

Arm 2: DURVALUMAB and TREMELIMUMAB

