7.1.7 Duration of Therapy

In the absence of unequivocal disease progression, as defined in Section 10.2.5, intolerable toxicity or withdrawal of consent to further participation, patients may continue to receive study treatment of durvalumab and tremelimumab at the discretion of the Investigator.

If, in the opinion of the Investigator, a patient is deriving clinical benefit from study therapy despite the documentation of objective disease progression per RECIST 1.1 criteria, then provided the patient does not have any significant, unacceptable, or irreversible toxicities that indicate that continuing treatment will not further benefit the patient, the patient may remain on study therapy pending their next disease assessment. However, appropriate imaging studies must be repeated within 4-8 weeks to re-assess treatment response. A patient with objective disease progression confirmed on subsequent assessment by either RECIST 1.1 criteria or Immune-Related Response criteria (irRC) as appropriate should be discontinued from the study. Patients should also be discontinued from the study if objective disease progression occurs in a target lesion that has previously shown a confirmed response.

For a complete list of general criteria for stopping study treatment, please see Section 10.0.

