7.6.3 Progression-free Survival

Progression-free survival (PFS) will be calculated for all patients from the day of randomization until the first observation of disease progression (date of objective relapse or progression of Relapse/Progression Report) or death due to any cause (recorded in Date/Cause of Death Section of Death Report) as the (difference+1).

If a patient has not progressed or died, PFS will be censored on the date of last disease assessment defined as the earliest test date of target lesion or non-target lesions (if patient has no target lesions), whichever is latest.

A frequency table will be provided describing progression and censoring as follows (**Table 35**):

- Number of patients who progress (documented progression, death without documented progression)
- Number of patients censored (alive and not progressed)

Analyses for PFS will be similar to that for overall survival as previously described. A Kaplan-Meier curve for PFS in each treatment arm will be displayed (**Figure 3**). In the primary analysis, median PFS for the two treatments will be compared using the stratified log-rank test (**Table 36**). A stratified Cox regression model will estimate the durvalumab and tremelimumab combined with best supportive care (ARM 2) over best supportive care alone (ARM 1) PFS hazard ratio and 90% C. I. (**Table 36**). In addition, a stratified Cox regression model adjusted for covariates will be applied to verify the impact of the prognostic factors on the treatment effect (**Table 36**).

Coding for treatment arm, stratification variables and prognostic factors is identical to that presented in **Section 7.5.1**.

Some patients received other anti-cancer therapy before progression or death. Sensitivity analyses will be performed by censoring those who have received anti-cancer therapy prior to documentation of disease relapse/progression or death on the earliest date cancer treatment began or treating them as having PFS events at the earliest date when the treatment began.

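### The protocol's PFS sensitivity analysis can re-date progression only in Arm 2, so a between-arm comparison on it would favour Arm 2; the SAP omits the analysis

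*Protocol*

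**What the plan says.** Protocol 13.2 defines PFS for both arms as "the time from randomization to the first objective documentation of disease progression or death due to any cause". It then adds a sensitivity analysis that counts time to "the second documentation of unequivocal disease progression in those patients who continued study therapy beyond the first objective documentation of disease progression", with the further condition "and with interim CR, PR or SD documented".

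Protocol 7.1.1 randomizes patients to "durvalumab plus tremelimumab plus best supportive care or best supportive care only to a planned sample size of 180". Section 7.1.7 shows what study treatment refers to: "patients may continue to receive study treatment of durvalumab and tremelimumab at the discretion of the Investigator". For a patient judged to benefit despite RECIST 1.1 progression, the same section says "the patient may remain on study therapy pending their next disease assessment" and requires repeat imaging within 4-8 weeks. Section 10.2 ends study therapy once progression is confirmed.

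The Arm 1 flowsheet (5.1) schedules scans "Every 8 weeks until objective disease progression (maintain schedule even if clinic visits are delayed". The Arm 2 flowsheet (5.2) has the same end point for scheduled scans.

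SAP 7.6.3 uses first progression or death as the PFS event. Its only sensitivity analyses concern other anti-cancer treatment: "Sensitivity analyses will be performed by censoring those who have received anti-cancer therapy prior to documentation of disease relapse/progression", or counting the start of that treatment as an event. The note under SAP Table 36 lists the same two.

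**The concern.** A sensitivity analysis of a randomized comparison should apply one event rule to both arms. This one excuses a first progression reading when the patient stayed on study drug and a later scan looked better. An Arm 1 patient has no study drug to stay on, so the same reading followed by the same course remains an event.

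Entry also depends on a favourable result after progression. The decision to continue rests on the investigator's opinion, in a trial that is open-label (SAP 2.1) and has no central radiology review (Protocol 11.1).

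If a between-arm hazard ratio were reported on this definition, it could be read as support for delayed immune benefit when part or all of it came from the rule.

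**Working it through.** **Plan's own figure.** The only design figure concerns overall survival (Protocol 13.3). Deaths = (1.645 + 0.842)² / [(2/3)(1/3)(ln 0.65)²] = 6.18 / (0.2222 × 0.1856) = 150, which matches the plan. Neither document gives a sample size or power for PFS, so this point does not contradict any stated figure.

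**Who can be re-dated.**

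| Requirement | Arm 2 | Arm 1 |
|---|---|---|
| Kept on study therapy past first progression (13.2) | Possible (7.1.7, 10.2) | Not possible: supportive care only (7.1.1) |
| Scheduled scans (5.1, 5.2) | End at objective progression | End at objective progression |
| Extra scan after progression | Within 4-8 weeks if kept on therapy (7.1.7) | None specified |
| Reporting form (Appendix IV) | Treatment Report while on treatment | Best Supportive Care Report ends at objective progression |

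The flowsheets treat the arms alike. The imbalance comes from the study-therapy condition and from the repeat scan in 7.1.7.

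**Direction.** Let T1 be the first progression and T2 the second, or the later death or censoring time. T2 cannot precede T1. Each re-dated Arm 2 time is therefore at least as long as before, and every Arm 1 time is unchanged.

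**Size.** Main simulation, with no treatment effect:
- From the documents: 120 v 60 patients (SAP 2.1), 8-weekly scans, and a two-sided 10% level, so nominally 5% of null trials favour Arm 2.
- Assumed: median PFS of 2 or 4 months; 15% of events are deaths; follow-up to 24 months; a share f of Arm 2 progressions re-dated by 16 or 32 weeks.
- Method: unstratified log-rank test, HR = exp[(O−E)/V], 600 trials per setting.
- Patients re-dated: about f × 0.85 × 120, that is 2 at f = 2%, 5 at 5%, 10 at 10% and 20 at 20%.

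Each cell shows the value before → after re-dating.

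| Median (months) | f | 16 weeks: HR | 16 weeks: Arm 2 wins | 32 weeks: HR | 32 weeks: Arm 2 wins |
|---|---|---|---|---|---|
| 2 | 2% | 0.999→0.971 | 6.0→7.8% | 0.983→0.934 | 6.2→10.2% |
| 2 | 5% | 0.991→0.923 | 5.8→12.3% | 0.982→0.863 | 6.0→16.8% |
| 2 | 10% | 0.987→0.860 | 6.0→16.7% | 0.996→0.782 | 3.2→34.2% |
| 2 | 20% | 1.001→0.767 | 4.8→36.8% | 0.977→0.622 | 7.0→73.3% |
| 4 | 2% | 0.996→0.983 | 5.5→6.3% | 0.996→0.971 | 5.0→6.2% |
| 4 | 5% | 0.982→0.951 | 7.2→9.3% | 0.980→0.920 | 6.2→11.8% |
| 4 | 10% | 0.995→0.934 | 4.5→10.8% | 0.986→0.873 | 7.2→20.5% |
| 4 | 20% | 1.011→0.891 | 5.2→15.8% | 1.009→0.790 | 5.3→33.8% |

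The before values vary by simulation error: for a 5% rate over 600 trials, √(0.05 × 0.95/600) = 0.9 percentage points. At f = 2% the excess is therefore small, and in some settings within noise. The HR moved toward Arm 2 in 99.8-100% of trials.

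Two further null simulations on other assumed settings agree on direction. One (median time to scan progression 2 months, median survival 4.5 months, 1,200 trials per f) gave HR 0.963, 0.924 and 0.862 with Arm 2 wins of 9.6%, 13.1% and 27.4% at f = 5%, 10% and 20%. The other gave HR 0.99, 0.94, 0.92 and 0.85 with wins of about 6%, 9%, 10% and 19% at f = 2%, 5%, 10% and 20%. Full settings for these two are not set out here, so they show only how far the size varies.

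**The case against.** **The SAP may govern, and it does not plan this analysis.** This stands as a limit on consequence: if only the SAP is followed, no biased result is produced. But the SAP does not withdraw the protocol's commitment, so the analysis could still be reported as pre-specified.

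**No between-arm test is named.** This also stands. The protocol says that the overall survival analyses will be repeated for PFS, but it says so before introducing this definition. The wording can be read as an analysis of continuing patients only. That reading contains no Arm 1 patients and gives no comparison. A reader might infer that the trial has committed itself to a biased hazard ratio, but the text does not go that far.

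**Scans.** A reader might infer that Arm 1 is disadvantaged because its flowsheet stops scans at progression. Both flowsheets do so, and the imaging difference comes from 7.1.7.

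**General wording on continued assessment.** Protocol 8.2 asks, without naming an arm, for assessments until progression is unequivocal. So it is too strong to say that no later Arm 1 scan could exist. But that paragraph is about continuing treatment, and an Arm 1 patient with a later scan showing stable disease would still fail the study-therapy condition.

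**Size.** The interim-response condition may make f small, and the documents give no rate. Large distortions should not be presented as expected.

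**Conclusion.** The rule is one-sided as written, and any comparison of arms on it is biased toward Arm 2. The direction follows from the definition. It is exact for individual PFS times, but not for every point of a Kaplan-Meier curve, since censoring between the two dates could lower a late part of the curve.

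The size is uncertain. Across the simulations, f = 2-5% gives HR about 0.86-0.99 and 6-17% false wins for Arm 2. For f = 10-20% the figures are HR about 0.62-0.93 and 10-73%. The share f, the PFS median and the re-timing delay are all assumptions.

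The definition also does not say how to treat a death, or a patient with no second progression.

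The primary overall survival analysis and PFS to first progression are untouched. With the SAP's silence, that makes this a minor point: an asymmetric secondary definition and a mismatch between protocol and SAP.

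**What to change.** In Protocol 13.2, do one of two things:

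1. Delete the sentence, which brings the protocol into line with SAP 7.6.3 and the Table 36 note.
2. Keep it in both documents as a descriptive summary of Arm 2 only. Report the number of patients whose first RECIST 1.1 progression was followed by a documented CR, PR or SD, and a Kaplan-Meier estimate of time to the second unequivocal progression or death. State that no between-arm hazard ratio or test is computed on this definition.

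Under either option, PFS to first RECIST 1.1 progression stays the comparative endpoint, as both documents already have it.

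The cost is wording only. The downside is that there is no comparative analysis on confirmed progression. That would need a matching rule and post-progression imaging in Arm 1, which its schedule does not provide, and randomization closed in June 2017 (SAP 2.1).
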